5.0 STUDY CONDUCT

5.1 Subject Disposition and Definition of Completers for Part 1 and Part 2

Subject disposition for Part 1 of the study will be summarized by treatment group and overall, where appropriate, for the All Screened Set. The following information will be reported:

- Number of subjects for the following category:
 - o Screened
- Number and percentage of subjects for the following categories:
 - o Randomized,
 - o Treated,
 - Not Treated.
 - o Completed Part 1 of the study,
 - o Ongoing in Part 1 of the study
 - o Discontinued from Part 1 of the study,
 - o Reasons for Part 1 study discontinuation.
- Number and percentage of subjects who failed and did not fail screening prior to randomization, including the primary reason for screen failure;

Subject disposition for Part 2 of the study will be summarized by treatment group and overall, where appropriate, for the All Enrolled Set, Part 2. The following information will be reported:

- Number and percentage of subjects for the following categories:
 - o Completed Part 2 of the study,
 - o Ongoing in Part 2 of the study
 - o Discontinued from Part 2 of the study,
 - o Reasons for Part 2 study discontinuation.

Moreover, the following information will be reported for the All Randomized Set, Part 1:

- Number and percentage of subjects included in each study population (All Randomized Set, Part 1; Efficacy Analysis Set, Part 1; Efficacy Analysis Set, Part 2; PPS, Part 1; Safety Analysis Set, Part 1; Safety Analysis Set, Part 2; BM Analysis Set, Part 1; and PK Analysis Set, Part 1);
- Number and percentage of subjects by country and site;

•	Number and	percentage of subjects by stratification	factors	
	region], and use of an MAOB Inh	ibitor [at Baseline). Each
		variable will be presented by the	collected in IV	VRS, except the use

of a MAOB Inhibitor at Baseline which will be presented both by the collected in IWRS and the collected in the eCRF.

Protocol Reference: CLR 18 06

The MAOB Inhibitors at the Baseline will be determined using the Chemical Subgroup (ATC-Level 4). The ATC-Level 4 that determines the MAOB Inhibitors is 'MONOAMINE OXIDASE B INHIBITORS' (ATC-Level 4 code: N04BD), based on WHO Drug Global Dictionary (version Mar 2022 or a later version if updated during the study), ATC Classification codes.

Completers of Part 1 and Part 2 of the study will be respectively defined as follows. A subject will be regarded as Part 1 completer if the subject attended the Visit 11 - Week 40 visit, at which the MDS-UPDRS Part III assessment on the subject was collected. A subject will be regarded as Part 2 completer if the subject attended the Visit 19 - Week 76 visit, at which the MDS-UPDRS Part III assessment on the subject was collected. A subject will be considered as having discontinued the study if the subject had an eCRF status of early study discontinuation. Otherwise, the subject will be considered as ongoing in the study.

A listing of all subjects with their treatment and study completion status, including the reason for study discontinuations, will be presented for the All Randomized Set, Part 1.

A listing of all screen-failed subjects with their reasons for screen failure will be presented for the All Screened Set. A separate listing of subjects who failed at least one inclusion/exclusion criteria, including a text description of the criterion failed, will be presented for the All Screened Set.

A listing of all randomized subjects with their randomization details, including first dose date and actual treatment received, will be presented for the All Randomized Set, Part 1.

A listing of all subjects with mis-stratification will be presented for the All Randomized Set, Part 1.

A listing of all subjects excluded from at least one analysis set will be presented for the All Randomized Set, Part 1.

5.2 Protocol Deviations

All important protocol deviations will be summarized for Parts 1 and 2 of the study separately, using the All Randomized Set, Part 1 and All Enrolled Set, Part 2, respectively, and all important protocol deviations leading to exclusion from the PPS, Part 1 (see Section 3.4.2) will be summarized for the Efficacy Analysis Set, Part 1 by treatment group and overall as described below:

for categorical variables.

The number of unique subjects with at least one important protocol deviation as well as the number of subjects in each important protocol deviation category, will be presented

[figure not shown]
Protocol Reference: CLR 18 06

The number of unique subjects with at least one important protocol deviation that led to exclusion from the PPS, Part 1 as well as the number of subjects in each important protocol deviation category, will be presented by default descriptive summary statistics

by default descriptive summary statistics for categorical variables.

A listing of the important protocol deviations will be presented for Parts 1 and 2 of the study

	ately, using the All Randomized Set, Part 1 and All Enrolled Set, and Part 2, respectively.
5.3	Measurement of Treatment Compliance
	cheduled visits , subjects are asked about compliance with study and any deviation in compliance could feed into a protocol deviation.
	umber of doses missed since the last visit is collected in the eCRF and taken into account e derivations of study exposure. Details regarding these derivations are provided in Section
5.4	Data Monitoring
T1	

6.0 DEMOGRAPHIC AND OTHER BASELINE CHARACTERISTICS

6.1 Demographic Characteristics

Demographic characteristics will be summarized for the All Randomized Set, Part 1, by treatment group and overall as described below. All missing data will be presented as part of a missing category, if appropriate. Standard descriptive statistics will be presented for the continuous variables of:

- Age at Screening (years)
- Weight (kg) at Screening
- Height (cm) at Screening
- Body mass index (kg/m²) at Screening (calculated as [body weight / height²] where weight is in kg and height is in m) and presented to one decimal precision

Total counts and percentages of subjects will be presented for the categorical variables of:

- Age group (years):
 - <= 65
 - > 65 to <= 75
 - >75
- Gender
- Childbearing potential (females only; classified as [yes], [no, surgically sterile], [no, post-menopausal], [no, other])
- Race
- Ethnicity
- Weight category (kg) at Screening:
 - <= 90
 - > 90 kg

6.2 Baseline Characteristics

Baseline characteristics will be summarized for the All Randomized Set, Part 1 by treatment group and overall as described below. All missing data will be presented as part of a missing category, if appropriate.

Standard descriptive statistics will be presented for the continuous variables of:

• Baseline MDS-UPDRS (Part I total score, Part II total score, Part III total score, the sum of the Parts II and III total scores, the sum of the Parts I, II and III total scores)

Protocol Reference: CLR 18 06

• Time between onset of PD symptoms and initiation of study

• Time between diagnosis of PD and initiation of the study

• Number of years of education

• Montreal cognitive assessment score at Screening

Total counts and percentages of subjects will be presented for the categorical variables of:

History of Sleep dysfunction

• History of Autonomic dysfunction

• History of Hyposmia

• History of Psychiatric dysfunction (

 Magnetic Resonance Imaging (MRI) scan of the brain suggestive of secondary Parkinsonism (

• DaT SPECT scan performed to determine eligibility conclusion:

• Meet criteria for clinically probable PD by MDS Clinical Diagnostic criteria:

• Serological tests:

• Hepatitis B Virus Surface Antigen:

• Hepatitis C Virus Antibody:

[figure not shown]
• Human Immunodeficiency Virus (HIV) 1 and 2 Antigen/Antibody:

• Smoking history:

• Alcohol consumption:

• Caffeine consumption:

• Currently working:

No formal tests of statistical significance will be performed on the demographic and baseline characteristics data.

6.3 Medical History

Medical history is defined as any condition, except for the study indication, that the subject may have had prior to enrollment in the study, including any chronic conditions diagnosed prior to entry in the study.

The medical history will be coded using the Medical Dictionary for Regulatory Activities (MedDRA) (version 23.0 or a later version if updated during the study) and will be presented by System Organ Class (SOC) and Preferred Term (PT).

Active medical history is defined as ticked on eCRF as ongoing (with or without treatment) and otherwise is defined as past.

Active and past medical history records will be summarized separately for the All Randomized Set, Part 1 by treatment group and overall as follows:

[figure not shown]
- The number and percentage of subjects with at least one active/past medical history record will be presented.
- The number and percentage of subjects with at least one active/past medical history record within each primary SOC and PT will be presented. The summary will be sorted using the internationally agreed order for SOC and using the descending order of overall numerical counts for PT. Where terms tie, these will be sorted alphabetically.

7.0 CONCOMITANT MEDICATIONS

It is expected that during the development of the study, the events defined in this section will take place. The aim of this section is to define flags to be created in the efficacy datasets and to facilitate the analysis of the efficacy endpoints as defined in Section 8.

7.1 Start Date of Symptomatic PD Medications for Part 1

The start of symptomatic PD medications will be derived according to the following algorithm:

The symptomatic PD medications will be selected using the following criteria from the WHODrug dictionary: ATC Class Level 2 equals to "ANTI-PARKINSON DRUGS" (Class code: N04).

For subjects on MAO-B inhibitors at baseline, the list of symptomatic PD medications will be the same as the above with the exclusion of the MAO-B inhibitors.

MAO-B inhibitors will be selected from the concomitant medications where ATC Class Level 4 equals to "MONOAMINE OXIDASE B INHIBITORS" (Class code: N04BD).

For subjects on MAO-B inhibitors at baseline, an increase from baseline in daily dose (mg/day) during Part 1 will be considered an intake of symptomatic PD medication as well.

(2) The date (in Part 1) when the first symptomatic PD medications were received or when an increase in the daily dose (mg/day) of MAOB inhibitors happened (whichever was the first occurrence) will be marked as the "symptomatic PD medications start date."

-641 - 6 -- 4 :- 4-1- - - 6 -- -- - 4 :- DD

Protocol Reference: CLR 18 06

(3) All visits or assessments with a date after the date of the first intake of symptomatic PD medication during Part 1 will be marked as "after the start date of symptomatic PD medications".

7.2 Start Date of Symptomatic PD Medications for Part 2

Subjects who started symptomatic PD medications in Part 1 will be withdrawn from the study and cannot enter Part 2. Subjects entering Part 2 are either still naïve to symptomatic PD medications or on MAO-B inhibitors (without an increase in dose) since the Part 1 baseline.

The start of symptomatic PD medications for Part 2 should be after the start of the study drug administration for Part 2. The start date of symptomatic PD medications for Part 2 will be derived and flagged using the same algorithm as above.

8.0 EFFICACY ANALYSES

All efficacy analyses for Part 1 (the double-blind treatment phase) of the study will be performed on the Efficacy Analysis Set, Part 1, and subjects will be included in the treatment group as randomized.

All efficacy analyses for Part 2 (the long-term extension phase) of the study will be performed on the Efficacy Analysis Set, Part 2, and subjects will be included in the treatment group as assigned at the baseline visit (Visit 13) of Part 2.

For all efficacy analyses, the values of stratification strata (for example, baseline user status of MAO-B inhibitors) as collected in the eCRF will be used instead of the values entered by the investigator into the IWRS, except for the supplementary analyses described in Section 8.1.6 below.

8.1 Primary Efficacy Analyses (Part 1)

The week 40 visit of Part 1 is a landmark time-point for this trial when the last assessment of the primary efficacy outcome for the double-blind treatment phase will be collected. The primary efficacy outcome variable is the MDS-UPDRS III total score, which is the sum of the rater-based Motor Examination (). The primary endpoint is the change from baseline to Week 40 in the MDS-UPDRS Part III total score.

8.1.1 Primary

This trial seeks to clarify the efficacy of K0706 in delaying the progress of PD in the ideal scenario of no intercurrent events and full adherence to the assigned 40-week treatment regimen dosed once daily in all randomized subjects. It is thus appropriate to employ the hypothetical for the primary efficacy analyses, with the use of a hypothetical strategy for handling intercurrent events. The primary is described by five attributes as follows.

- **Treatment**: the treatment condition of interest includes the high dose and the low dose of K0706 in formulation administered once daily for 40 weeks. The alternative treatment condition to which the comparison will be made is Placebo in formulation administered once daily for 40 weeks.
- Target Population: subjects aged ≥ 50 years in whom an initial diagnosis of PD was within 3 years of the screening visit, who score on a modified Hoehn and Yahr stage ≤ 2, who meet the protocol-specified inclusion and exclusion criteria.
- Endpoint: Change from Baseline to Week 40 in the MDS-UPDRS Part III total score

Statistical Anal	ysis Plan	CONFIDENTIAL	
			Protocol Reference: CLR_18_06
• •			
virtual visits (directly or income handled COVID-19 pandemic had used to clarify	or say, remote assessment directly related to the pand. Sub-	ts) and possibly early disc lemic. Virtual visits in the ojects who dropped out for s if they would have drop hetical strategy for handlind there been no occurrence	pandemic environment will not r a reason related to the ped out for other reasons if the mg will be
8.1.2 M	ethod of Estimation		
Mean changes	s from baseline in the MD	S-I IPDRS Part III score v	will be analyzed using the
Wiedir change.	s from baseline in the MD	5-01 DRS 1 art III score v	The analysis will be
will be the destreatment arm interaction ter the interaction covariates. Ar In case of the	change from the baseline is pendent variable based on a, analysis visit, region (), base on of treatment by analysis a term of baseline Part III	eline MAOB inhibitor uses visit as the fixed, categors score by analysis visit as structure will be used to model with	er status (and the orical effects, and will include the continuous, fixed model the within-subject error.
		to t	he best fit will be used as the
primary analy	rsis.		no oest ne win oo used us the
dose and the printeraction ter	ee contrasts of group mean booled dose of the K0706 cm of treatment by analysiserve as the primary comp	vs. placebo) at Week 40 vs visit based on the parison. Test of significan	square means for each active will be estimated from the

Statistical Analysis Plan CONFIDENTIAL Protocol Reference: CLR_18_0
each contrast will be constructed. The analysis will be implemented using the
In addition to the above main estimates at Week 40, the LS mean and its CI for each treatment group, together with the LS mean difference and its CI and p-value for the comparison of each active dose and the pooled dose of K0706 versus placebo at each post-baseline visit prior to Week 40 will be extracted from the same A negative value of the contrast estimate with Placebo as the reference group would clinically favor the K0706 group.
The Part III total score at baseline and at each post-baseline visit and the change from baseline will also be summarized by the treatment group using standard descriptive statistics. Mean values of the Part III total score together with their CI or SE, will be plotted over time (weeks) by treatment group.
8.1.3 Subgroup Analyses for the Primary Efficacy Endpoint
Two subgroups of interest are defined as follows. with the mild motor-predominant subtype at baseline. () proposed clinical criteria for dividing PD patients into based on a of the data on the de novo treatment-naïve PD patients from the study The proposed criteria will be adapted to define The Proseek cohort is considerably similar in demographics and baseline disease characteristics to the de novo PD cohort in the study This similarity justifies the use of the subtyping criteria developed by
is defined as having the composite motor score and all the three non-motor scores below the where the is the sum of the MDS-UPDRS Part II and III total scores, and the three non-motor scores are of SCOPA-AUT, MoCA and Rapid Eye Movement Sleeping Disorder (RBDSQ) respectively.
is obtained by excluding subjects of the mild motor-predominant subtype from the Efficacy Analysis Set (for Part 1 period) (Appendix 3).

Statistical Analysis Plan	CONFIDENTIAL	D
		Protocol Reference: CLR_18_06
		_
		_
		
•		
•		
•		
 		
).		

Statistical Analysis Plan	CONFIDENTIAL	
		Protocol Reference: CLR_18_06
 		
S		
9		
90		
Raw (unadjusted) p-va	alues for individual hypotheses will be ext	tracted from the
for the	The state of the s	the two comparisons at
	itilizing the correlation of the test statistics	Control of the contro
in the same of the	for the randomization ratio 1:1:	_
8.1.5 Supplement	ntary Analysis Addressing the Effect of	a
10.0	subjects may have conflicting values in the	
MAO-B inhibitors usa		t data sources (eCRF versus
IWRS). If such a perc		p, the primary efficacy analysis
will be repeated by us	ing the values from the IWRS.	
017	Parameter and the second	
8.1.6	Analyses	
The mean change-from	n-baseline at Week 40 in the MDS-UPDR	S Part III score will be analyzed
by using		effect, and with baseline Part III
total score, region	with a camen as a fixed main	and baseline MAOB
total score, region		and ouseful in top
17		

inhibitors user status (from eCRF) as covariates. Of note, the change-from-baseline data at Week 40 will be imputed using approach for the above analysis. The primary efficacy analyses will be repeated on the Per Protocol Set, Part 1. If any clinical sites are identified by audit as having had non-compliance issues prior to database lock, the primary efficacy analyses will be repeated on the data excluding the non-compliant sites. The distribution-free permuation test () will be used to test the robustness of the overall treatment effect (for the pairwise comparison of each dose group, and the pooled dose group vs the placebo group) over repeated assessments of the primary efficacy outcome during Part 1. Specifically, the for the observed mean difference at each post-baseline assessment will be calculated, and thus the mean over repeated assessments will be calculated based on the actual data of the trial. In order to calculate the corresponding p-value, the permutation test will be conducted in which subjects will be permuted randomly (without breaking repeated observations at each subject) between 3 treatment arms. The process will be times in order to construct frequency distribution for the simulated p-value for each pairwise comparison (using the placebo group as the reference group) will be computed by calculating the percentage of the simulated mean favorable (i.e., having larger treatment effect) than the actual observed mean p-value tends to support the presence of the overall treatment effect over multiple assessments. analysis will be examined. If the model fit calls into question, Model fit of the primary analyses will be performed post-hoc. If the dropout rate is differential across treatment groups, additional analyses will be performed post hoc. 8.2 **Secondary Efficacy Analyses** 8.2.1

Part 1 (Day 1 to Week 40)

The secondary efficacy variables or endpoints of interest for Part 1 of the study are as follows.

- Change from baseline through Week 40 in the sum of the MDS-UPDRS Parts II and III total scores.
- Change from baseline through Week 40 in the MDS-UPDRS Part IA sub-score, Part IB sub-score, Part I total score, Part II total score, and the four sub-scores of Part III
- Change from baseline through Week 40 in the grand sum of the MDS-UPDRS Parts I, II and III total scores.

- Evaluation of slopes of the mean change in MDS-UPDRS Parts III total score over time during Part 1 by treatment group.

8.2.1.3 Time to Event Analysis

 To determine if K0706 slows early-stage PD progression by increasing the time to significant worsening of PD, as compared to placebo.

The event of interest is the significant worsening of PD during Part 1.
\geq
 
AEs associated with PD symptoms will be identified by using the following AE preferred terms:
based
on MedDRA version 23.0 or newer. The final list of preferred terms associated with PD
symptoms will be provided in the 'Analysis Set Specification' document.

withdrawal due to PD-related AEs, as compared to placebo.

The event of interest consists of two sub-events as follows.	

Statistical Analysis Plan CON	FIDENTIAL	Protocol Reference: CLR_18_06
AEs. Subjects without the event of interest we event analyses will be similar to that describe		rule and the time-to- aragraph.
 To determine if K0706 delays the init compared to placebo. 	iation of symptomati	c PD medications, as
The event of interest is the initiation of symposubsection, Subjects without the event of interest time-to-event analyses will be similar to that	erest will be censored	l. The rule and the
 To determine if K0706 delays the wort total scores, as compared to placebo. 	rsening of PD in term	ns of the MDS-UPDRS Part III
The event of interest is the increase Part III total score. Subjects without the even and the time-to-event analyses will be similar	t of interest will be	baseline in the MDS-UPDRS The rule the preceding paragraph.
8.2.1.4		, ,
's		
		a

[figure not shown]
Statistical Analysis Plan C	ONFIDENTIAL Protocol Reference: CLR 18 00
•	
•	

• To evaluate the effect of K0706 on skin pathology markers of PD.

• To evaluate the effect of K0706 on blood and cerebrospinal fluid (CSF) biomarkers linked to PD and target engagement of K0706.

The specific blood and CSF biomarkers (parameters) linked to PD have not yet been fully determined at the time of the writing of this SAP. Potential parameters may include α -synuclein, total Tau, ratio of total Tau/ α -synuclein, amyloid, etc. For each parameter, graphical displays in the forms of mean plots and Tukey box and whisker plots will be used to summarize the data by dose group and visit.

In addition, the statistical correlation of each biomarker parameter with the efficacy endpoint will be explored in the following ways. (1) Pearson's and Spearman's correlation coefficient (and its CI) between the change-from-baseline parameter value and the change-from-baseline MDS-UPDRS Part III score at the end of Part 1 (Week 40) will be estimated. (2) Subjects will be divided into 3 categories (roughly corresponding to "worse off," "little changes", and "improvement") with respect to the primary clinical outcome. Unless otherwise specified, the tertiles of change-from-baseline at Week 40 in the Part-III score will be used as the cutoffs. Tukey's box and whisker plots of the change-from-baseline at Week 40 in each biomarker parameter will be plotted by category of the primary clinical outcome.

• To investigate genetic and clinical markers that predict the degree of progression of early-stage PD and / or response to K0706.

Specific genetic and clinical biomarkers (parameters) may be identified as potential candidates predictive of the degree of progression of early-stage PD. For each parameter, the exploratory analyses will be similar to those in the preceding paragraph.

 To evaluate the effect of K0706 on dopamine cell health in PD as detected via Dopamine Transporter Single Photon Emission Computed Tomography (DaT SPECT) brain imaging.

DaT SPECT brain imaging will be performed at baseline and at the EOT visit (Week 40). The following parameters or quantities may be of relevance: left caudate Striatal Binding Ratio (SBR), right caudate SBR, left putamen SBR, right putamen SBR, and minimum putamen SBR, etc. For each parameter, the exploratory analyses will be similar to those in the preceding paragraph.

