5.0 STUDY DESIGN

5.1 Description of Type and Design of Study

This is a randomized, multicenter, double-blind, placebo-controlled, study to evaluate the efficacy, safety, and tolerability of two dose levels of K0706 in subjects with early PD who are not receiving symptomatic therapy. This study consists of two parts. Part 1 is designed to evaluate the efficacy, safety, and tolerability of two dose levels of K0706 compared to placebo in subjects with early stage PD. Part 2 is an optional long-term extension study assess the long-term safety/tolerability of K0706 in subjects with early PD. Part 1 Subjects will visit the clinic for the part 1 Screening Visit, be screened based on the eligibility criteria, and provide written informed consent. Confirmation of eligibility at the Part 1 Baseline visit will require the availability of laboratory results, as well as Investigator interpretation of Magnetic Resonance Imaging (MRI) of the brain and central reading of a DaT SPECT scan (obtained prior to or as part of this study). . The screening period is summarized in the Screening Period Flow Diagram (Figure 17-1). Following confirmation of eligibility at the Part 1 Baseline visit, all subjects will be randomized, have baseline assessments performed, and receive the first dose of the study drug. This will be followed by planned visits as per the Schedule of Assessments. The part 1 treatment assessment for efficacy will be performed at Week 40. Subjects choosing not to continue in part 2 will return for a follow-up visit at Week 44. Subjects will provide blood for the measurement of standard safety laboratory parameters and of levels of K0706.

If a subject chooses to begin taking symptomatic PD medication during the trial, they will be discontinued from the study and will be asked to come in for an Early Discontinuation (ED) visit for their final assessment. They will be requested to perform this visit prior to initiation of symptomatic medication. The date of initiation of symptomatic medication will be documented appropriately in source notes and eCRF.

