4.2.1 Handling of Missing Efficacy Data

In general, missing efficacy	data will not be imputed for efficacy analyses. The analyses
will be based on	The only exception is that a set of supplementary
	of the primary efficacy variables at Week 40 will be
performed on	imputed data.

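### The exploratory marker analyses in SAP 8.3.1 use only subjects with an observed Week 40 Part III score; for baseline markers, the slope model already planned would use the data of those who leave earlier

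*SAP*

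**What the plan says.** **Outcome used.** SAP 8.3.1 estimates Pearson and Spearman correlations between change in the marker and the "change-from-baseline MDS-UPDRS Part III score at the end of Part 1 (Week 40) will be estimated". It then forms three categories, labelled 'worse off', 'little changes' and 'improvement': "Unless otherwise specified, the tertiles of change-from-baseline at Week 40 in the Part-III score will be used as the cutoffs". The display is of marker change too: "box and whisker plots of the change-from-baseline at Week 40 in each biomarker parameter will be plotted by category".

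**Carried over to predictors.** For genetic and clinical markers that may be "predictive of the degree of progression of early-stage PD. For each parameter, the exploratory analyses will be similar to those in the preceding paragraph". DaT SPECT, done at baseline and Week 40, gets the same treatment.

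**Who lacks the outcome.** Protocol 5.1: "If a subject chooses to begin taking symptomatic PD medication during the trial, they will be discontinued from the study". SAP 7.2 confirms that such subjects are withdrawn and cannot enter Part 2. Protocol 5.1 also asks for an Early Discontinuation (ED) visit: "They will be requested to perform this visit prior to initiation of symptomatic medication".

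**Missing data.** SAP 4.2.1 states that in general missing efficacy "data will not be imputed for efficacy analyses". The one exception is a supplementary analysis of the primary variable. The visible text of 8.3.1 has no rule for subjects without a Week 40 value.

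**The concern.** Starting symptomatic medication is not a neutral reason for missing data. Protocol 2.3.6 treats time to starting it as an indirect measure of worsening disability, and both documents analyse it as an efficacy endpoint. An event that counts toward worsening in SAP 8.2.1.3 therefore takes the subject out of the progression measure in 8.3.1.

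Baseline markers are the clearest case. Genotype or a baseline clinical score is known for every leaver who was tested, and Part III scores before medication will often exist. Only the choice of a single Week 40 outcome excludes them. A genotype also has no change from baseline, so an instruction to analyse it in a similar way already needs spelling out.

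At stake is the exploratory objective on markers that predict progression or response, which Protocol 2.3.1 expects to inform phase 3 design. No primary or confirmatory result depends on it.

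**Working it through.** There is no figure in the plan to reproduce: the documents give no marker sample size, expected correlation or medication-start rate for this analysis. Every rate below is an assumption. The only related statement, in Protocol 2.3.1, is that most early-stage subjects can be expected to stay off dopamine replacement for 40 weeks.

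**Step 1. Number affected.** If all 506 randomized subjects were in the marker set (an upper bound), 5%, 10%, 20% and 30% leaving is 506 × 0.05, 0.10, 0.20 and 0.30, or about 25, 51, 101 and 152 subjects.

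**Step 2. Effect on the correlation when leaving is linked to the marker only through Week 40 change.** Let the true marker-change correlation be ρ = 0.30. The top fraction d of a latent drive to start medication leaves, and that drive correlates k with Week 40 change. With c = Φ⁻¹(1 − d), λ = φ(c)/(1 − d) and δ = λ(λ + c), the correlation among those who remain is

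r = ρ √[(1 − k²δ)/(1 − ρ²k²δ)].

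Example, d = 0.20 and k = 0.7: c = 0.842, λ = 0.350, δ = 0.417, k²δ = 0.204, so r = 0.30 × √(0.796/0.982) = 0.270.

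| Leaving | δ | r, k = 0.3 | r, k = 0.7 | r, k = 1 |
|---|---|---|---|---|
| 5% | 0.190 | 0.298 | 0.287 | 0.272 |
| 10% | 0.288 | 0.296 | 0.280 | 0.257 |
| 20% | 0.417 | 0.295 | 0.270 | 0.233 |
| 30% | 0.507 | 0.294 | 0.263 | 0.216 |

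With k = 0 there is no bias. A simulation of 1,000,000 draws agrees to within 0.002. For 5% to 20% leaving and k of 0.3 to 0.7 the relative loss is about 1% to 10%.

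**Step 3. When marker and leaving both track an underlying progression** that Part III measures with 70% reliability (assumed), and s is the correlation of leaving with that progression:

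r = 0.30(1 − s²δ)/√[(1 − (0.09/0.7)s²δ)(1 − 0.7s²δ)].

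At d = 0.20 and s = 0.8, s²δ = 0.267 and r = 0.30 × 0.733/√(0.966 × 0.813) = 0.248. Over 10% to 30% leaving and s of 0.6 to 0.8, r is 0.235 to 0.281. At 5% leaving it is 0.278 to 0.288.

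**Step 4. Power, separating bias from lost subjects.** Power = Φ(atanh(r)√(n − 3) − 1.96). With 100 subjects measured (assumed) and r = 0.30 it is 86%. Losing 10%, 20% or 30% of subjects with no bias gives 82%, 78% and 72%. Adding the Step 3 bias gives 50% to 77%. A good part of the fall is fewer subjects.

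**Step 5. Tertiles.** Cut-offs are recomputed in those who remain. Under the Step 2 model, with k of 0.3 to 0.7, the upper cut-off moves from 0.43 SD to between 0.37 and 0.28 SD at 10% leaving, and to between 0.32 and 0.16 SD at 20%. The share of the true top third that is lost is 16% to 25% and 30% to 45% respectively.

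**Step 6. Candidate remedies.**
- *Ranking leavers worst.* In the Step 3 model, full-data Spearman is 0.287. At s = 0.3, completers only versus leavers ranked worst gives 0.282 versus 0.261 (10% leaving) and 0.279 versus 0.232 (20%). At s = 0.8 and 10% leaving the order reverses, 0.252 versus 0.288. A separate simulation at 20% leaving and selection 0.3 also favoured completers, 0.183 versus 0.154.
- *Pre-medication slopes, baseline markers.* In a simulation with linear progression assumed, 5% to 30% leaving and selection 0 to 0.8, slopes gave higher power than the Week 40 completer correlation in every case (for example about 68% to 79% at N = 200, 20% leaving, selection 0.3). They gave an equal or higher correlation in all cases but one (0.187 versus 0.195 at 30% leaving unrelated to progression).

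**The case against.** The case against is substantial.

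- **Some leavers may have a Week 40 value.** An ED visit is requested before medication starts, and SAP 4.1.4.1 windows unscheduled as well as scheduled assessments. The Week 40 range is not visible. A reader might infer that leavers cannot have the score; the documents support only that they generally will not.
- **Few may leave, and for mixed reasons.** Besides the expectation in Protocol 2.3.1, inclusion criterion 6 screens out subjects projected to need early dopaminergic therapy. Protocol 2.3.6 notes that work status and physician preference also affect starting. That stands, and it is why the size cannot be fixed.
- **The direction is likely, not certain.** If leaving also depends on the marker in the opposite direction, a correlation of 0.30 rises to about 0.34 (10% leaving) or 0.35 (20%). If the marker plateaus in fast progressors it hardly moves.
- **For marker change at Week 40, leavers usually lack the marker as well.** This includes DaT SPECT. No outcome definition recovers them.
- **Redaction and flexibility.** The description of the biomarker analysis set breaks off, the tertile rule allows for other specification, and Protocol 9.6.3 permits post-medication scores in exploratory analyses. Part of a rule may exist out of view, though the visible 8.3.1 text does not take up that permission.

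What remains is the baseline-marker case: the predictor is known, earlier scores will often exist, and the planned outcome does not use them.

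**Conclusion.** The point holds as a cheap improvement to an exploratory analysis. As visibly written, SAP 8.3.1 is complete-case at Week 40, and the trial's own rationale links the main design-driven cause of missingness to progression. This costs precision and probably biases associations toward zero if leaving tracks progression. The bias is about 1% to 10% in relative terms at 5% to 20% leaving under the simpler model. It is larger if leaving follows underlying progression closely (0.30 to 0.25 at 20% leaving and selection 0.8). Leaving rate, selection strength, reliability, true correlation and marker sample size are all assumed.

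Two stronger readings are not supported. One is that the fastest progressors vanish and the 'worse off' group is emptied: tertiles are re-cut, so the group is filled with milder change, by an amount the documents do not let us fix. The other is that medication starters should simply be counted as worst: that does more harm than the planned analysis when leaving is only loosely tied to progression, which the protocol's remarks on confounding make plausible.

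**What to change.** In SAP 8.3.1:

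1. For genetic, clinical and other baseline markers, make the Part III slope from the random-coefficients model in SAP 8.2.1 the main progression measure, either as a marker-by-time term or as each subject's slope. Use all pre-medication scores, including the ED visit.
2. Keep the Week 40 completer correlations and tertile plots as a secondary display.
3. For baseline markers, add a sensitivity display with medication starters placed in 'worse off', not as the main rule.
4. Report the number of subjects excluded from each Week 40 analysis. For marker change at Week 40, including DaT SPECT, this count is all that can be added.

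The cost is a few sentences and modest programming. The scores are already scheduled and the model already specified. The downside is that slopes of early leavers are less precise, and subject-level slopes shrink toward the mean.
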